### 9.2.1.2. Serious Adverse Event

A serious AE (SAE) is any untoward medical occurrence that at any dose:

- Results in death
- Is life-threatening (an event which places the patient at immediate risk of death from the event as it occurred; it does not include an event that had it occurred in a more severe form might have caused death)
- Requires inpatient hospitalization or prolongation of existing hospitalization
- Results in persistent or significant disability/incapacity
- Is a congenital anomaly or birth defect
- An important medical event that may not be immediately life-threatening or result in death or hospitalization but may jeopardize the patient or may require intervention to prevent one of the other outcomes listed in the definition above (eg, such events include allergic bronchospasm, blood dyscrasias or convulsions, or the development of drug dependency or abuse)

### 9.3. Relationship to Study Drug

Causal relationship assessment to drug treatments is required for purposes of reporting AEs. To promote consistency, the following guidelines should be taken into consideration along with good clinical and scientific judgment when determining the relationship of drug treatments to an AE:

- Definitely Related: A clinical event, including laboratory test abnormality, occurring in a plausible time relationship to the medication administration, and which cannot be explained by concurrent disease or other drugs or chemicals. The response to withdrawal of the drug should be clinically plausible.
- Possibly Related: A clinical event, including laboratory test abnormality, with a reasonable time sequence to the medication administration, but which could also be explained by concurrent disease or other drugs or chemicals. Information on the drug withdrawal may be lacking or unclear.
- Unlikely Related: A clinical event, including laboratory test abnormality, with little or no temporal relationship to medication administration, and which other drugs, chemicals, or underlying disease provide plausible explanations.
- Not Related: A clinical event, including laboratory test abnormality, that has no temporal relationship to the medication or has more likely alternative etiology.

### 9.4. Recording Adverse Events

The patient should be asked about medically relevant changes in his/her health since the last visit. The patient should also be asked if he/she has been hospitalized, had any accidents, used any new medications, or changed concomitant medication routines (both prescription and OTC).

In addition to patient observations, AEs will be documented from any clinically relevant laboratory findings, physical examination findings, or other findings.

Adverse events are to be graded according to the categories detailed below.

Mild: Mild events are those which are easily tolerated with no disruption of normal daily activity.

Moderate: Moderate events are those which cause sufficient discomfort to interfere with daily activity.

Severe: Severe events are those which incapacitate and prevent usual activity.

Changes in severity should be documented in the medical record to allow assessment of the duration of the event at each level of severity. Adverse events characterized as intermittent require documentation of the start and stop of each incidence. When changes in the severity of an AE occur more frequently than once a day, the maximum severity for the experience that day should be noted. If the severity category changes over a number of days, then those changes should be recorded separately (with distinct onset dates).

## 9.5. Reporting Adverse Events

The Investigator is responsible for reporting all AEs that are observed or reported after the first dose of patisiran regardless of their relationship to patisiran administration through the end of the study.

Any medical condition that is present when the patient enters this extension study and does not deteriorate should not be reported as an AE. However, if it does deteriorate at any time during the study, it should be reported as an AE.

All AEs must be fully recorded in the site's source records and in the patients' CRF, whether or not they are considered to be drug-related. Each AE should be described in detail: onset time and date, description of event, severity, relationship to investigational product, action taken, and outcome (including time and date of resolution, if applicable).

Adverse events should be followed through the end of study visit or until recovery to the normal state has been achieved, whichever occurs first. In the event of a patient not returning to the clinical unit, the outcome of this event will be recorded as lost to follow-up.

For patients who withdraw from the study early, ongoing AEs will be followed until resolution or 28 days from last dose, whichever occurs first. SAEs will be followed by the Investigator until satisfactory resolution or the Investigator deems the SAE to be chronic or stable.

### 9.5.1. Serious Adverse Event Reporting

An assessment of the seriousness of each AE will be made by the Investigator. Any AE and laboratory abnormality that meets the above seriousness criteria (Section 9.2.1.2) must be reported immediately to the CRO, always within 24 hours from the time that site personnel first learn of the event. All SAEs must be reported regardless of the relationship to patisiran.

The initial report should include at least the following information:

- Patient's study number

- Description and date of onset of the event
- Criterion for serious
- Preliminary assignment of causality

Serious AE reporting will be via electronic data capture (EDC).

To report the SAE, complete the SAE form electronically in the EDC system for the study. If the event meets serious criteria and it is not possible to access the EDC system, send an email to Medpace Safety at PPD or call the Medpace SAE hotline listed below (country-specific phone number will be provided in the Study Manual), and fax the completed back-up paper SAE form to Medpace (country-specific fax number will be provided in the Study Manual) within 24 hours of awareness. When the form is completed, Medpace Safety personnel will be notified electronically and will retrieve the form. When the EDC system becomes available, the SAE information must be entered into the EDC system within 24 hours of the system becoming available. Medpace Safety personnel will be available for SAE reporting on a 24 hour basis. Incoming reports will be reviewed during normal business hours.

Medpace SAE hotline – USA:

Telephone: PPD ext. PPD or PPD ext. PPD  
Facsimile: PPD or PPD

Medpace SAE hotline – Europe:

Telephone: PPD  
Facsimile: PPD

Within 24 hours of receipt of follow-up information, the investigator must update the SAE form electronically in the EDC system for the study and submit any supporting documentation (eg, patient discharge summary or autopsy reports) to Medpace Safety personnel via fax or e-mail. If it is not possible to access the EDC system, refer to the procedures outlined above for initial reporting of SAEs.

Appropriate remedial measures should be taken by the Investigator using his/her best medical judgment to treat the SAE. These measures and the patient's response to these measures should be recorded. All SAEs, regardless of causality, will be followed by the Investigator until satisfactory resolution or the Investigator deems the SAE to be chronic or stable. Clinical, laboratory, and diagnostic measures should be employed by the Investigator as needed to adequately determine the etiology of the event.

The Investigator will be responsible for reporting all SAEs to the local IEC or IRB when required by national regulations.

The Sponsor or its representative will be responsible for the reporting of all relevant events to the concerned regulatory authorities according to all applicable regulations.

In Europe, in accordance with the Directive 2001/20/EC, the Competent Authorities and the Ethics Committees in the concerned Member States will be notified of fatal and life-threatening Suspected Unexpected Serious Adverse Reactions (SUSARs) as soon as possible but no later than 7 calendar days after the Sponsor or its representative has first knowledge of the minimum criteria for expedited reporting. Non-fatal and non-life-threatening SUSARs should be reported no later than 15 calendar days after the Sponsor or its representative has first knowledge of them.

The Investigator may be informed by the Sponsor or its representative of SAEs from other Investigators or clinical studies which may have relevance to this clinical study. These SAEs should also be reported promptly to the IEC/IRB that approved the study. All SAE reports should be transmitted to the IEC/IRB with a cover letter or transmittal form, and a copy of that transmittal should be maintained in the Investigator's files and forwarded to the Sponsor as part of the trial master file on study completion.

### **9.5.2. Pregnancy Reporting**

A female patient must have a negative pregnancy test within 14 days before the first dose of patisiran on this study. If a female patient is found to be pregnant during the course of the study or during the first month after receiving the last dose of patisiran, the Investigator should report the pregnancy to the CRO within 24 hours of being notified of the pregnancy. Details of the pregnancy will be recorded on the pregnancy reporting form. Treatment with patisiran will be discontinued in any patient who is found to be pregnant during the study. The patient should receive any necessary counseling regarding the risks of continuing the pregnancy and the possible effects on the fetus.

The pregnancy should be followed by the Investigator until completion. At the completion of the pregnancy, the Investigator will document the outcome of the pregnancy. If the outcome of the pregnancy meets the criteria for an SAE (ie, postpartum complication, spontaneous abortion, stillbirth, neonatal death, or congenital anomaly), then the Investigator should follow the procedures for reporting an SAE outlined above.

Pregnancy occurring in the partner of a patient participating in the study should also be reported to the Investigator, who will then report this to the CRO and follow to outcome as described above.

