**Table 1 Schedule of Assessments**

	Day 0 Visit	12 Week Visit	26 Week Visit	52 Week Visit	Annual Visit	End of Study	Early Withdrawal Visit
	Window ≤45 Days from Last Dose a	±4 Weeks	±4 Weeks	±4 Weeks	±6 Weeks	4 (+1) Weeks from Last Dose	4 (+1) Weeks from Last Dose
Procedure							
Informed Consent	X						
Inclusion/Exclusion Criteria	X						
Medical History	X b						
Demographics	X c						
Physical Examination	X d			X	X	X o	X o
Weight	X Prior to Each Dose					X o	X o
mBMI e	X d			X	X	X o	X o
Height	X c						
FAP Stage and PND Score	X d			X	X	X o	X o
Karnofsky Performance Status	X						
NYHA Classification	X			X			[X] f
Vital Signs g	X Prior to Each Dose						
Safety Laboratory Assessments h	X d	X	X	X	X	X	X
INR	X						
Pregnancy Test (urine)	X i		X	X	X	X	X
C-SSRS Questionnaire			X	X	X	X	X

	Day 0 Visit	12 Week Visit	26 Week Visit	52 Week Visit	Annual Visit	End of Study	Early Withdrawal Visit
	Window	≤45 Days from Last Dose a	±4 Weeks	±4 Weeks	±4 Weeks	±6 Weeks	4 (+1) Weeks from Last Dose
Procedure							
TTR Protein (ELISA)	X d		X	X	X	X	X
TSH and Vitamin A				X	X	X o	X o
Blood Sample for Long-term Storage	X	X	X	X	X	X	X
mNIS+7 j	X d			X			[X] f
NIS+7 k	X d			X			[X] f
NIS only					X l	X m	X m
Grip Strength Test n	X d			X			[X] f
10-Meter Walk Test p	X d			X			[X] f
Ophthalmology Examination q	X d			X	X	X o	X o
Skin Punch Biopsy (IENFD and SGNFD) r				X	X	X o	X o
MR Neurography s ( Germany & France only )	X		X	X	X	X o	X o
Pharmacoeconomics Questionnaire	X			X	X	X o	X o
Norfolk QOL-DN t	X d			X	X	X o	X o
COMPASS 31 Questionnaire	X d			X			[X] f
R-ODS Disability	X d			X			[X] f
EQ-5D QOL	X d			X	X	X o	X o
Echocardiogram	X d,u			X			[X] f
Troponin I and NT-proBNP	X d			X			[X] f

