### 1.2. Patisiran

Patisiran (the International Nonproprietary Name [INN] name for the drug product also referred to as ALN-TTR02) is a novel investigational agent being developed for the treatment of ATTR patients with symptomatic FAP. Patisiran comprises a small interfering ribonucleic acid (siRNA) which is specific for TTR, and is formulated in a hepatotropic lipid nanoparticle (LNP) for intravenous (IV) administration. It is designed to significantly suppress liver production of both WT and all mutant forms of TTR, thereby having the potential to reduce amyloid formation and provide clinical benefit to patients with FAP.

The nonclinical pharmacology, pharmacokinetics (PK), and toxicology of patisiran were evaluated in a series of in vitro and in vivo studies that have enabled chronic dosing in clinical studies. A summary of the nonclinical data can be found in the patisiran Investigators Brochure (IB).

In a Phase 1 study of patisiran in healthy volunteers (Study ALN-TTR02-001), patisiran was generally well tolerated. Significant pharmacology in terms of TTR protein lowering (>80% reduction from pretreatment baseline) was observed at doses  $\geq 0.15$  mg/kg. TTR levels showed evidence of recovery at Day 28 and return to baseline by Day 70. A Phase 1 study in healthy

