## 4. SELECTION AND WITHDRAWAL OF PATIENTS

### 4.1. Patient Inclusion Criteria

To be enrolled in the study, patients must meet the following criteria before administration of patisiran on Day 0:

1. Have completed a patisiran study (ie, completed the last efficacy visit in the parent study) and, in the opinion of the investigator, tolerated study drug
2. Be considered fit for the study by the Investigator
3. Have aspartate transaminase (AST) and alanine transaminase (ALT) levels  $\leq 2.5 \times$  the upper limit of normal (ULN), international normalized ratio (INR)  $\leq 2.0$  (patients on anticoagulant therapy with an INR of  $\leq 3.5$  will be allowed)
4. Have a total bilirubin within normal limits. A patient with total bilirubin  $\leq 2 \times$  ULN is eligible if the elevation is secondary to documented Gilbert's syndrome (elevation of unconjugated bilirubin with normal conjugated bilirubin) and the patient has ALT and AST levels within normal ranges.
5. Have a serum creatinine  $\leq 2 \times$  ULN
6. Women of child-bearing potential must have a negative pregnancy test, cannot be breastfeeding, and must be using 2 highly effective methods of contraception prior to dosing in this study and agree to use 2 highly effective methods of contraception throughout study participation and for 75 days after last dose of patisiran in this study. Highly effective methods of birth control are defined in Section 4.4.
7. Males with partners of child-bearing potential must agree to use 1 barrier method (eg, condom) and 1 additional method (eg, spermicide) of contraception throughout study participation and for 75 days after the last dose of patisiran in this study; males must also abstain from sperm donation after the first dose of patisiran through study participation and for 75 days after last dose of patisiran in this study
8. Be willing and able to comply with the protocol-required visit schedule and visit requirements and provide written informed consent

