### 4.4. Pregnancy and Breastfeeding Restrictions / Contraception Requirements

TTR transports vitamin A in plasma; therefore, reductions in circulating vitamin A levels accompany reductions in TTR caused by patisiran. Vitamin A deficiency has known effects on both male and female reproductive performance and embryo/fetal development. It is not known whether decreased levels of vitamin A at efficacious patisiran doses in ATTR patients who are male or who are women of child bearing potential will affect reproduction. Histopathological evaluations of all of the reproductive organs have been conducted in the rat and non-human primate (NHP) toxicology studies including a chronic NHP study in sexually mature animals, where there were no adverse effects in males (including sperm analyses and spermatogenic staging) or females. In a dose range-finding rat embryo/fetal development study

conducted with patisiran, there were no effects on mating, fertility, ovarian or uterine parameters, or fetal development despite reductions (-88% from baseline) in serum vitamin A in the dams dosed with the rat-specific TTR surrogate siRNA.

Women of child-bearing potential are defined as any woman or adolescent who has begun menstruation. A post-menopausal woman is defined as a woman who has 12 months of spontaneous amenorrhea or 6 months of spontaneous amenorrhea with serum FSH levels >40 mIU/mL or 6 weeks postsurgical bilateral oophorectomy with or without hysterectomy.

In this study, women of child-bearing potential must have a negative pregnancy test, cannot be breastfeeding, and must be using 2 highly effective methods of contraception prior to dosing on Day 0, throughout study participation, and for 75 days after last dose of patisiran in this study. Highly effective methods of birth control result in a low failure rate (ie, less than 1% per year). Acceptable forms of effective contraception are defined as follows:

- Hormonal: established use of oral, implantable, injectable, or transdermal hormonal methods of conception
- Placement of an intrauterine device (IUD)
- Placement of an intrauterine system (IUS)
- Mechanical/barrier method of contraception: condom or occlusive cap (diaphragm or cervical/vault cap) in conjunction with spermicide (foam, gel, film, cream or suppository)

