Males (including men who have had vasectomies) with partners of child-bearing potential, must agree to use 1 barrier method (eg, condom) and 1 additional method (eg, spermicidal foam, gel, film, cream, or suppository) of contraception throughout study participation and for 75 days (ie, a whole spermatogenic cycle) after the last dose of patisiran in this study. Males must also abstain from sperm donation after the first dose of patisiran through study participation and for 75 days after last dose of patisiran in this study.

In Japan it is recommended that the Investigators select appropriate contraception methods, as available.

Pregnancy reporting guidelines are provided in Section [9.5.2](#).

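### For female patients the duty to report a pregnancy ends about one month after the last dose, while the protocol requires contraception for 75 days after it

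*Protocol*

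**What the plan says.** Section 9.5.2 (Pregnancy Reporting) sets the trigger for female patients: "If a female patient is found to be pregnant during the course of the study or during the first month after receiving the last dose". The post-dose part, with the duty attached to it, reads: "during the first month after receiving the last dose of patisiran, the Investigator should report the pregnancy to the CRO within 24 hours". Such a pregnancy is then followed to completion, and is handled as an SAE if its outcome meets the SAE criteria.

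Inclusion criterion 6 in Section 4.1 requires women of child-bearing potential to "agree to use 2 highly effective methods of contraception throughout study participation and for 75 days after last dose of patisiran in this study". Section 4.4 repeats the period: "throughout study participation, and for 75 days after last dose of patisiran in this study". Men with partners of child-bearing potential have the same length, with an explanation: "for 75 days (ie, a whole spermatogenic cycle) after the last dose of patisiran in this study".

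For partners, Section 9.5.2 says only: "Pregnancy occurring in the partner of a patient participating in the study should also be reported to the Investigator". The investigator then reports to the CRO and follows to outcome. No end date is given.

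In Table 1 the End of Study and Early Withdrawal visits, which carry the last scheduled urine pregnancy test, fall at "4 (+1) Weeks from Last Dose". General adverse event reporting under Section 9.5 stops at the end of the study.

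The one-month and 75-day periods are the same in every protocol version in the file, including Version 3.1 for the United Kingdom.

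**The concern.** The protocol asks women to avoid pregnancy for 75 days after the last dose but asks investigators to report a pregnancy only if it is found in about the first 30 of those days. A contraceptive failure that surfaces later falls inside the precaution and outside the data collection. Nothing else picks it up: the last test is at 4 to 5 weeks, and adverse event reporting has ended by then. Follow-up to completion and SAE handling of the outcome both start from the pregnancy report, so without a report no passage requires either.

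Section 4.4 itself says that vitamin A deficiency is known to affect reproduction and embryo/fetal development, and that whether the lower levels seen with patisiran do so in these patients is unknown. The study's objective includes long-term safety, and pregnancies are likely to be few. Losing even one outcome to a drafting mismatch would be avoidable.

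**Working it through.** No sample size, power or alpha bears on this point. The check compares two periods, both counted from the last dose.

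**Inputs**
- Post-dose contraception period, women: 75 days (Sections 4.1 and 4.4).
- Post-dose reporting limit, female patients: the first month (Section 9.5.2). The protocol does not define a month, so 28, 30 and 31 days are tried.
- Last scheduled visit: 4 (+1) weeks, that is 28 to 35 days (Table 1). If the course of the study is read as running to this visit, reporting could reach day 35.

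**Formulas**
- Uncovered days = 75 − reporting limit in days.
- Uncovered share = uncovered days / 75.

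| Reading of the limit | Uncovered days | Share of 75 days |
|---|---|---|
| 28 days (4 weeks) | 75 − 28 = 47 | 62.7% |
| 30 days | 75 − 30 = 45 | 60.0% |
| 31 days | 75 − 31 = 44 | 58.7% |
| 35 days (End of Study visit at 5 weeks) | 75 − 35 = 40 | 53.3% |

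Under each of these readings more than half of the post-dose period is uncovered.

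These shares count by the date on which the pregnancy is found, because that is how Section 9.5.2 words the limit. A conception in the first month that is recognised later also falls outside. Counted by date of conception, the figures above are therefore minimums.

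If reporting for female patients ran for the full 75 days, the uncovered part by date found would be 75 − 75 = 0 days.

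**The case against.** Five arguments on the other side deserve weight, and most of them limit what can be claimed.

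**Denominator.** A reader might infer that most of the protocol's whole risk window goes unreported. It does not. Contraception is required throughout participation as well as after it, and reporting covers all of participation. For a patient who completes the estimated 5 years, the period is about 5 × 365 + 75 = 1,900 days, and a 45-day gap is about 2.4% of it. The shares above describe the post-dose tail only. Pregnancies found during dosing bear at least as directly on the safety question, and they are reported and followed.

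**Partners.** A reader might extend the one-month limit to all pregnancies. It is written for female patients. The partner sentence states no limit, so putting a 75-day cap on it could reduce capture. What stands is that describing the patient as participating in the study leaves its reach after the last dose unclear.

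**Pharmacology.** It is tempting to argue from Section 1.2, "TTR levels showed evidence of recovery at Day 28 and return to baseline by Day 70", that vitamin A is still lowered for most of the gap. That statement concerns TTR in healthy volunteers. It gives no vitamin A time course, and nothing for patients after long-term dosing. The only explanation the protocol attaches to 75 days is a spermatogenic cycle, which concerns men. The point does not need the pharmacological argument.

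**Different purposes.** Contraception and reporting rules serve different ends, and a site can comply with both, so this is a misalignment and not a strict contradiction. That is fair. Even so, a reporting period shorter than the precaution omits failures of that same precaution, and the protocol gives no reason for the difference.

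**Course of the study.** This could mean the whole trial, not the patient's own participation. For a patient who leaves early, the separate one-month clause would then have little purpose. The ambiguity is itself worth removing.

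**Conclusion.** The point holds, limited to female patients after their last dose. Followed as written, Section 9.5.2 leaves 40 to 47 of the 75 post-dose contraception days (53% to 63%) with no duty to report a pregnancy found then or to follow it to outcome.

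The range rests on a month of 28 to 31 days, or on reporting that runs to an End of Study visit at 5 weeks, and on reading the course of the study as the patient's own participation. The finding says nothing about the treatment period, which is covered, and it does not claim that partner pregnancies are cut off at one month.

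This concerns a short post-treatment tail of what is likely to be a rare event, so it is a modest point. It is still worth correcting, because the protocol calls the reproductive effect unknown and the correction costs very little. Which duration is clinically right is not judged here; the sections need to be reconciled.

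**What to change.** Reconcile Section 9.5.2 with Sections 4.1 and 4.4 so that the reporting period for female patients is at least as long as the post-dose contraception period the protocol states. Referring to that period in Section 9.5.2, without restating a number, would keep the two from drifting apart. The sentence should also say whether the period is counted by when the pregnancy is found or by when it was conceived. At the final visit, tell the patient to notify the site of a pregnancy during that period.

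For partner pregnancies, add no cap. Clarify only that the existing duty to report continues after the patient's last dose, for at least the stated contraception period.

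The cost is a short protocol amendment and matching consent wording. No visit, test, dose or contraception rule changes.
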